8.1.4. Analysis of Period Data (Time to Event Onset)

The median, first quartile, and third quartile by Kaplan-Meier method will be calculated. In addition, Kaplan-Meier plots will be prepared.

8.2. Statistical Analysis

8.2.1. Overview of Patients

- **Number of sites by establisher and number of patients**

In patients for whom the case report form was collected, the number and proportion of sites by establisher shown below and the number and proportion of patients will be calculated.

- University hospitals
- National hospitals established by the Ministry of Health, Labour and Welfare
- Prefectural and municipal hospitals
- Public organizations
- Hospitals other than the above four established by corporations and individuals
- General practitioners/clinics

In addition, the mean, minimum, and maximum will be calculated for the number of patients per site.

- **Dispositions of patients**

In patients who completed the study, the number of patients included in the analysis of safety, the number of patients included in the analysis of clinical response, and the number of patients included in the analysis of mycological response will be tabulated. In addition, the number of patients excluded from the analysis of safety, clinical response, and mycological response and the number of patients by reason for exclusion will be tabulated.

- **Listing of discontinuations and dropouts**

In the safety analysis set, the number and proportion of patients who discontinued or completed (cured) treatment by Week 16 will be tabulated by timing [<1 week, ≥ 1 to <2 weeks, ≥ 2 to <4 weeks, ≥ 4 to <8 weeks, ≥ 8 to <12 weeks, ≥ 12 to ≤ 16 weeks]. In addition, the number and proportion of patients by reason for discontinuation will be tabulated by timing.

- **Listing of excluded patients**

The listing of patients excluded from the analysis of safety, clinical response, and mycological response and reasons for exclusion will be prepared.

8.2.2. Patient Background and Treatment History of Vfend

- **Patient background**

In the safety analysis set, clinical response analysis set, and mycological response analysis set, the following patient background factors will be tabulated in accordance with Section 8.1.

- Sex [male, female]
- Age (continuous; years)
- Age (children 1) [newborns (<1 month after birth), infants (≥ 1 month to <1 year), younger children (≥ 1 to <7 years), children (≥ 7 to <15 years)]
- Age (children 2) [<2 years, ≥ 2 years]
- Body weight (continuous; kg)
- Hospitalized Status [inpatient, outpatient]
- Presence or absence of fever unresponsive to antibacterial agents [absent, present]

- Objective of treatment [treatment of mycosis, others]
- Severity [mild, moderate, severe]
- Presence or absence of prior treatment with antifungal agents [absent, present]
- Presence or absence of hepatic dysfunction [absent, present, unknown]
- Severity of hepatic dysfunction [mild, moderate, severe, unknown]
- Presence or absence of renal dysfunction [absent, present, unknown]
- Severity of renal dysfunction [mild, moderate, severe, unknown]
- Presence or absence of past medical history [absent, present]
- Presence or absence of concurrent illness [absent, present]
- Diagnostic name (name of infection) [invasive aspergillosis, pulmonary aspergilloma, chronic necrotic pulmonary aspergillosis, candidemia, esophageal candidiasis, candida peritonitis, bronchopulmonary candidiasis, cryptococcal meningitis, pulmonary cryptococcosis, fusariosis, scedosporiosis, other invasive fungal infections, others*]
- Diagnostic name (definitive diagnosis)** [invasive aspergillosis, pulmonary aspergilloma, chronic necrotic pulmonary aspergillosis, candidemia, esophageal candidiasis, candida peritonitis, bronchopulmonary candidiasis, cryptococcal meningitis, pulmonary cryptococcosis, fusariosis, scedosporiosis, other invasive fungal infections]

*: Patients will basically be classified based on the name of infection, but patients for whom the diagnostic name is others will be classified as “others.”

**: Definitive diagnosis: When the final diagnosis by the physician is invasive fungal infection

In the safety analysis set, the number and proportion of the following patients will be tabulated by System Organ Class (SOC) and Preferred Term (PT) of MedDRA.

- Past medical history
- Concurrent illness

In the safety analysis set, clinical response analysis set, and mycological response analysis set, the number and proportion of the following patients will be tabulated.

- Concomitant medications
- Contraindicated concomitant medications
- Concomitant medications requiring precautions for coadministration
- Prior treatment (antifungal agents) for infection for which Vfend is administered
- Reasons for discontinuation of prior treatment for infection for which Vfend is administered

- **Status of treatment of Vfend**

In the safety analysis set, the following status of treatment of Vfend will be tabulated: Furthermore, dose will be tabulated separately for patients aged <12 years and ≥12 years

whose body weight is less than 50 kg and those aged ≥ 12 years whose body weight is 50 kg or more.

- Treatment period [<1 week, ≥ 1 to <2 weeks, ≥ 2 to <4 weeks, ≥ 4 to <8 weeks, ≥ 8 to <12 weeks, ≥ 12 to ≤ 16 weeks, >16 weeks]
- Treatment period (long-term treatment) [≤ 12 weeks, >12 weeks]
- Treatment period (days) (continuous)
- Dose on the first day (mg) (continuous)
- Dose on the first day (mg) [<50 , ≥ 50 to <100 , ≥ 100 to <150 , ≥ 150 to <200 , ≥ 200 to <250 , ≥ 250 to <300 , ≥ 300 to <350 , ≥ 350 , unknown]
- Dose on the first day (mg/kg) (continuous)
- Dose on the first day (mg/kg) [<6 , ≥ 6 to <7 , ≥ 7 to <8 , ≥ 8 to <9 , ≥ 9 to <10 , ≥ 10 , unknown]
- Mean maintenance dose (mg) (continuous)
- Mean maintenance dose (mg) [<50 , ≥ 50 to <100 , ≥ 100 to <150 , ≥ 150 to <200 , ≥ 200 to <250 , ≥ 250 to <300 , ≥ 300 to <350 , ≥ 350 , unknown]
- Mean maintenance dose (mg/kg) (continuous)
- Mean maintenance dose (mg/kg) [<6 , ≥ 6 to <7 , ≥ 7 to <8 , ≥ 8 to <9 , ≥ 9 to <10 , ≥ 10 , unknown]
- Mean maintenance dose of injection alone (mg) (continuous)
- Mean maintenance dose of injection alone (mg) [<50 , ≥ 50 to <100 , ≥ 100 to <150 , ≥ 150 to <200 , ≥ 200 to <250 , ≥ 250 to <300 , ≥ 300 to <350 , ≥ 350 , unknown]
- Mean maintenance dose of injection alone (mg/kg) (continuous)
- Mean maintenance dose of injection alone (mg/kg) [<6 , ≥ 6 to <7 , ≥ 7 to <8 , ≥ 8 to <9 , ≥ 9 to <10 , ≥ 10 , unknown]
- Mean maintenance dose of oral preparations (tablet + dry syrup) alone (mg) (continuous)
- Mean maintenance dose of oral preparations (tablet + dry syrup) alone (mg) [<50 , ≥ 50 to <100 , ≥ 100 to <150 , ≥ 150 to <200 , ≥ 200 to <250 , ≥ 250 to <300 , ≥ 300 to <350 , ≥ 350 , unknown]
- Mean maintenance dose of oral preparations (tablet + dry syrup) alone (mg/kg) (continuous)
- Mean maintenance dose of oral preparations (tablet + dry syrup) alone (mg/kg) [<6 , ≥ 6 to <7 , ≥ 7 to <8 , ≥ 8 to <9 , ≥ 9 to <10 , ≥ 10 , unknown]

The treatment period is from the initial day of administration in this study to the last confirmed day of administration, including the period during which Vfend is suspended.

If treatment with Vfend is continued at the end of the observation period, the treatment period will be considered as 113 days because Vfend is administered for >16 weeks (Week 16 is up to Day 112 with the day of initiation of treatment considered as Day 1).

8.2.3. Safety Analysis

Adverse drug reactions and adverse events observed during the observation period (from the day of initiation of Vfend treatment to the day of completion of treatment) + follow-up period (28 days*) or if the treatment prolongs, during the period from the initiation of treatment to Week 16 (Day 112 counting from Day 1 as the day the treatment begins) will be tabulated. If the duration of the observation period + follow-up period exceeds 112 days, events observed by Day 112 will be tabulated. All events reported in this study will be included in listings.

*: The duration of the follow-up period in this investigation was set at 28 days because a 30-day follow-up period was provided in a clinical study (Study A1501096) and the period of collection of adverse events using NIS AE Report Form in this investigation is up to 28 days after the day of completion of treatment.

8.2.3.1. Adverse Drug Reactions

- **All adverse drug reactions**

The number and proportion of patients with adverse drug reactions will be tabulated by SOC and PT. Also by diagnostic name (name of infection), the number and proportion of patients with adverse drug reactions will be tabulated by SOC and PT.

- **Serious adverse drug reactions**

The number and proportion of patients with serious adverse drug reactions will be tabulated by SOC and PT. In addition, the number and proportion of patients by known/unknown serious adverse drug reactions will be tabulated by SOC and PT.

- **Details of adverse drug reactions**

The number and proportion of patients with adverse drug reactions will be tabulated by SOC and PT for each of the following items.

- Seriousness [serious, non-serious]
- Known/unknown [known, unknown]
- Intervention [discontinuation, temporarily discontinued, dose reduction]
- Outcome [not recovered, recovered with sequela, recovering, resolved/recovered, unknown]

In addition, the number and proportion of patients with adverse drug reactions meeting all of the following conditions will be tabulated by SOC and PT.

- Seriousness is “non-serious”
- Intervention is “discontinuation,” “temporarily discontinued,” or “dose reduction”
- Outcome is “not recovered” or “recovered with sequela”

If the same adverse event (the same PT) occurs more than once in the same patient, it will be handled as follows in the tabulation of the number of patients with events:

- Seriousness: If both serious and non-serious events are reported, “serious” will be adopted.
- Known/unknown: If both known and unknown events are reported, “unknown” will be adopted.
- Number of days to onset: The number of days to the first event will be adopted.
- Intervention: If multiple types of action taken with Vfend for the adverse events are reported, one of discontinuation, temporarily discontinued, dose reduction, or none, in descending order of precedence, will be adopted.
- Outcome: The outcome of the last occurring event will be used.

- **Safety specifications**

The number and proportion of patients with events will be tabulated. In addition, the number and proportion of patients with safety specifications by intervention and outcome will be tabulated by SOC and PT.

- **Major investigation items**

The number and proportion of patients with major investigation items will be tabulated. The number and proportion of patients with major investigation items by intervention (change in treatment with Vfend) and outcome will be tabulated by SOC and PT.

The number and proportion of patients with adverse drug reactions considered as major investigation items will be calculated by intervention (change in treatment with Vfend) to assess whether treatment with Vfend was discontinued because of the onset of the adverse drug reaction after its onset.

The listing of patient background and concomitant medications will be prepared in patients with major investigation items with high incidence to evaluate factors common to patients with major investigation items.

- **Timing of onset of adverse drug reactions**

The number of patients with major investigation items and adverse drug reactions observed in $\geq 10\%$ of patients will be tabulated by SOC and PT by timing of initial onset [<1 week, ≥ 1 to <2 weeks, ≥ 2 to <4 weeks, ≥ 4 to <8 weeks, ≥ 8 to <12 weeks, ≥ 12 to ≤ 16 weeks].

For major investigation items and adverse drug reactions observed in $\geq 10\%$ of patients, time to event onset will be summarized in accordance with Section 8.1.4 with the initial onset of the adverse drug reaction considered as an event. Patients without adverse drug reactions will be censored after the observation period + follow-up period (28 days). Patients for whom the duration of the observation period + follow-up period exceeds 112 days will be censored at Day 112.

- **Relationship between concomitant medications and development of adverse drug reactions**

The number of patients with hepatic toxicity and visual events will be tabulated overall and by PT by presence or absence of actually used concomitant medications to evaluate the relationship of contraindicated concomitant medications and concomitant medications requiring precautions for coadministration with adverse drug reactions considered as major investigation items. However, medications started to be used after the day of the last onset of the event during the observation period + 28 days will be excluded from tabulation.

In addition, the number of patients with adverse drug reactions will be tabulated by SOC and PT by presence or absence of actually used concomitant medications to evaluate the relationship of contraindicated concomitant medications and concomitant medications requiring precautions for coadministration with adverse drug reactions. However, medications started to be used after the day of the last onset of the adverse drug reaction during the observation period + 28 days will be excluded from tabulation.

- **The adverse drug reactions by patients of included/excluded in the safety analysis set**

In patients for whom the case report form was collected, the listing of adverse drug reactions in patients excluded from the safety analysis set will be prepared. The number of patients with events will be tabulated by SOC and PT.

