7.2.6. Observation period

The observation period shall start on the day the treatment with this product begins and end on the day the treatment is completed; provided that it will be cut off at Week 16 of treatment (Day 112 counting from Day 1 as the day the treatment begins) if the treatment prolongs.

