7.3.8. Adverse events

Confirm the status of adverse events from the initiation of treatment with this product to the completion of observation period, and record the following information. Upon discovery of an adverse event, the attending doctor should take appropriate actions, and promptly report to Pfizer Japan Inc. (hereinafter "Sponsor"), and if causal relation with this product cannot be ruled out, the doctor should follow up the event until the adverse event or its sequelae are resolved or stabilized at the level acceptable by the attending doctor and Sponsor.

Moreover, a study should be conducted on patients in whom a serious adverse reaction, or an adverse reaction not specified in the package insert occurred if it is determined necessary by Sponsor.

- (1) Presence/absence of adverse event
- (2) Name of adverse event
- (3) Date of occurrence
- (4) Action
- (5) Seriousness
- (6) Outcome
- (7) Causality

[If the adverse event is associated with abnormal change in laboratory values, i.e., laboratory tests, the following information should also be recorded.]

- (1) Laboratory parameter
- (2) Site reference value
- (3) Unit
- (4) Date of test
- (5) Results

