7.6. Data management

7.6.1. Data collection method

Data for this study shall be collected using a specific case report form provided by Pfizer. Investigator will complete promptly after observation period and submit them to the Pfizer.

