9. MANAGEMENT AND REPORTING OF ADVERSE EVENTS/ADVERSE REACTIONS

The handling of each event in the case where the investigator becomes aware of any event concerning the safety information should be prescribed as follows:

For an event that needs to be reported to the sponsor within 24 hours, the investigator must report it using the designated "Non Interventional study AE Report Form (hereinafter referred to as "NIS AE Report Form")

At the initiation of study, each staff in charge of each site shall request each investigator to report events that need to be reported within 24 hours of discovery, and visit the investigator periodically within the study period to request for reporting.

The NIS AE Report Form will be handled as part of the case report form.

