9.1. REQUIREMENTS

The table below summarizes the requirements for recording safety events on the case report form and for reporting safety events on the non-interventional study (NIS) adverse event monitoring (AEM) Report Form to Pfizer Safety. These requirements should be described for the following 3 types of events.(1) serious adverse events (SAEs); (2) non-serious AEs (as applicable); and (3) scenarios involving exposure to a Pfizer product, including exposure during pregnancy, exposure during breast feeding, medication error, overdose, misuse,

extravasations, and occupational exposure. These events are defined in the section “Definitions of safety events”.

Safety event	Recorded on the case report form	Reported on the NIS AE Report Form to Pfizer Safety within 24 hours of awareness
SAE	All	All
Non-serious AE	All	None.
Scenarios involving exposure to a Pfizer product, including exposure during pregnancy, exposure during breast feeding, medication error, overdose, misuse, extravasation; lack of efficacy; and occupational exposure	All (regardless of whether associated with an AE), except occupational exposure	All (regardless of whether associated with an AE) involving exposure to a Pfizer product

For each AE, the investigator must pursue and obtain information adequate both to determine the outcome of the adverse event and to assess whether it meets the criteria for classification as a SAE (see section "Serious Adverse Events" below)

Safety events must be reported to Pfizer within 24 hours of awareness of the event by the investigator as described in the table above. In particular, if the SAE is fatal or life-threatening, notification to Pfizer must be made immediately, irrespective of the extent of available event information. This timeframe also applies to additional new (follow-up) information on previously forwarded safety event reports. In the rare situation that the investigator does not become immediately aware of the occurrence of a safety event, the investigator must report the event within 24 hours after learning of it and document the time of his/her first awareness of the events.

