9.2. Reporting period

For each patient, the safety event reporting period begins at the time of the patient's informed consent, which is obtained prior to the patient's registration in the study, and lasts through the end of the observation period of the study; a report must be submitted to Pfizer Safety (or its designated representative) for any of the types of safety events listed in the table above occurring during this period. If a patient was administered a drug under study on the last day of the observation period, then the reporting period should be extended for 28 calendar days following the end of observation.

If the investigator becomes aware of a SAE occurring at any time after completion of the study and s/he considers the serious AE to be related to a Pfizer product, the SAE also must be reported to Pfizer Safety.

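### The Kaplan-Meier rule counts event-free patients at risk for up to 28 days after treatment, without a last-contact stop and without established collection of non-serious reactions in those days

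*SAP*

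**What the plan says.** SAP 8.2.3.1 (timing of onset) plans Kaplan-Meier curves and quartiles for hepatic toxicity, visual events and any adverse drug reaction seen in at least 10% of patients. These are not restricted to serious events. The censoring rule is "Patients without adverse drug reactions will be censored after the observation period + follow-up period (28 days", with a cap at Day 112. It matches the tabulation window in SAP 8.2.3, to which version 5.0 aligned it. One of the two reasons that SAP 8.2.3 gives for the 28 days is that "the period of collection of adverse events using NIS AE Report Form in this investigation is up to 28 days" after treatment is completed. The other is a 30-day follow-up in a different study.

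On collection, the protocol says:
- 7.2.6: "The observation period shall start on the day the treatment with this product begins and end on the day the treatment is completed", with a cut-off at Day 112.
- 7.3.8: "Confirm the status of adverse events from the initiation of treatment with this product to the completion of observation period".
- 7.6.1, on the case report form: "Investigator will complete promptly after observation period and submit them to the Pfizer".
- 9.1 (table): non-serious events are all recorded on the case report form, but the entry is *None* in the column headed "Reported on the NIS AE Report Form to Pfizer Safety within 24 hours of awareness".
- 9.2: if the drug was given on the last day of observation, "the reporting period should be extended for 28 calendar days following the end of observation".
- 9: "The NIS AE Report Form will be handled as part of the case report form".

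Protocol 7.3.6 lists no revisit and hospital transfer among the reasons for discontinuation. The censoring rule makes no exception for these patients or for deaths.

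**The concern.** A Kaplan-Meier curve is valid only if an event during time counted at risk would have been recorded. Here up to 28 days are added for every event-free patient. If non-serious reactions are not sought in those days, the denominator keeps patients in whom such an event could not be seen. The estimated hazard is then too low, and the quartiles come out late or are not reached.

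The outputs at stake are the onset curves and quartiles for the two major investigation items. A crude proportion does not use time at risk, so the censoring rule does not change it. Incomplete collection would, however, also leave the SAP 8.2.3 tables short of events for the same window.

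**Working it through.** **1. The plan's own figures.** The documents give no Kaplan-Meier result to reproduce. The rates used below come from Protocol 7.5.2: 4 patients (19.0%) with hepatic toxicity and 9 (42.9%) with visual events, which implies 21 patients. With these rates and 100 patients, P(X ≥ 13) = 0.958 for hepatic and P(X ≥ 35) = 0.956 for visual, so the stated counts of 13 and 35 reproduce.

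**2. Days added.** For treatment length D the rule adds min(D + 28, 112) − D days.

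| D | days added | time at risk ÷ treatment time |
|---|---|---|
| 7 | 28 | 35/7 = 5.0 |
| 14 | 28 | 42/14 = 3.0 |
| 28 | 28 | 56/28 = 2.0 |
| 84 | 28 | 112/84 = 1.33 |
| 100 | 12 | 112/100 = 1.12 |
| 112 | 0 | 1.0 |

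**3. Is a non-serious reaction collected in those days?**

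| Against | For |
|---|---|
| Protocol 7.3.8 and 7.2.6: events confirmed to the end of treatment | Protocol 9.2: 28-day extension, for any event type listed in the 9.1 table |
| Protocol 7.6.1: form completed soon after observation | Protocol 9: NIS AE form counts as part of the case report form |
| Protocol 9.1: no non-serious events on the NIS AE form | Protocol 9.3: events of unknown causality must be reported |
| | SAP 10.1: completion laboratory value may be taken on or after the last dose, with no upper limit |

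The right-hand column makes some capture likely. Nothing in it says that capture of non-serious reactions is complete.

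**4. Size.** The documents do not give treatment length, off-drug hazard or capture, so these are assumed: exponential treatment length with median 28 days (rate μ = ln 2/28 = 0.02476 per day), constant on-drug hazard h, and the rates above taken as on-treatment rates. That last step is approximate, because the source study had 30 days of follow-up. Solve

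h/(h+μ) × [1 − exp(−112(h+μ))] = p.

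- Visual, p = 0.429: h = 0.01885. Check: 0.4322 × 0.9924 = 0.429.
- Hepatic, p = 0.190: h = 0.00604. Check: 0.1962 × 0.9682 = 0.190.

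Under the SAP rule the observed hazard is λ(t) = [h·on(t) + g·off(t)] / [on(t) + off(t)]. Here on(t) = exp(−(h+μ)t), off(t) = ∫ μ exp(−(h+μ)d) exp(−g(t−d)) dd for d from max(0, t−28) to t, and g is the off-drug hazard of captured reactions. The curve is exp(−∫λ). Results are rounded up to whole days.

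| | visual median | hepatic first quartile |
|---|---|---|
| SAP rule, nothing captured (g = 0) | Day 70 | Day 87 |
| Full capture, off-drug hazard zero | Day 70 | Day 87 |
| Full capture, off-drug hazard 10% of h | Day 62 | Day 79 |
| Full capture, off-drug hazard 25% of h | Day 54 | Day 70 |
| Full capture, off-drug hazard unchanged | ln 2/h = Day 37 | −ln 0.75/h = Day 48 |

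The error against the SAP's own window is row 1 minus the row that is true: zero at zero hazard, 16 and 17 days at 25%, 33 and 39 days if the hazard is unchanged. At 25% with median treatment of 14 or 56 days, the visual median is 65 against 32, or 90 against 81. The hepatic first quartile is 76 against 45, or 108 against 98.

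Hazard shape also matters. With a 10-fold hazard in week 1, no capture and the off-drug hazard otherwise unchanged, the visual first quartile does not move (Day 5 in both), but the median is Day 104 against 50.

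**5. Losses alone.** If everyone else is fully captured and the off-drug hazard is unchanged, the visual median moves from Day 37 to 39 with 10% lost and to 43 with 30% lost. At 100 patients the sampling range of that median is about Day 26 to 55.

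**The case against.** The strongest reply is that the *None* in Protocol 9.1 only exempts non-serious events from 24-hour reporting, since the same row puts all of them on the case report form. Protocol 9.2 extends reporting by 28 days for every listed event type, and its condition is normally met because observation ends on the last treatment day. This stands to the extent that no capture is an extreme case. It does not establish complete capture: 7.3.8 is not extended, and 9.2 starts its period at an informed consent that 8.1 says is not used.

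A reader might infer that non-serious reactions are definitely not collected after treatment. The documents do not support that; they are ambiguous.

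A reader might also take Day 70 against 37 as the bias and want the curve censored at end of observation to replace the SAP's. Those two curves answer different questions, and the same contrast appears when there is no bias at all. In the 25% case the end-of-observation curve is about as far from the SAP window as the current rule: 37 against 54 (17 days early), compared with 70 (16 late). For the hepatic first quartile it is 22 days early, compared with 17 late.

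Two further points stand. SAP 5.1(e) already removes patients with no visit after the first prescription day and no adverse event information, though not later losses. The stakes are also low: Protocol 7.7 names no time-to-event analysis, and the SAP has no decision rules.

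**Conclusion.** The point holds in a limited form. The censoring rule credits event-free patients with up to 28 days that the documents do not show to be observed for non-serious reactions, and it does not stop at loss or death. The direction is clear if reactions occur and are missed: incidence too low, quartiles too late. The size cannot be fixed from the documents. Under the stated assumptions with no capture, the visual median is late by 0 to 33 days and the hepatic first quartile by 0 to 39 as the off-drug hazard runs from zero to unchanged. Partial capture shrinks the gap. The missing last-contact rule is a defect however collection is settled, but its effect alone is small.

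**What to change.** 1. In SAP 8.2.3.1, censor event-free patients at the earliest of last contact or death, end of observation + 28 days, and Day 112. The protocol lists no last-contact date, so for no revisit and hospital transfer use the end of observation unless a later dated contact is held.
2. Add a Kaplan-Meier curve censored at the end of observation, labelled as a sensitivity analysis of on-treatment onset. Keep the existing window for the main curve.
3. Reconcile Protocol 7.3.8, 7.6.1, 9, 9.1, 9.2 and 9.3 with SAP 8.2.3 on which events, serious and non-serious, are collected in the 28 days. If non-serious collection is incomplete, say so beside both the main curve and the SAP 8.2.3 tables.

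The cost is SAP wording, a re-derived censoring date and one extra curve per event. Post-treatment reactions are absent from the added curve but remain in the main curve and the tables.
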